8.7 TC-3

Telephone Contact-3 is only applicable to subjects who have completed Visit 13 and should be conducted 2 weeks after the final dose of BRV.

- Concomitant medications including AEDs
- AEs

8.8 Unscheduled Visit

If an Unscheduled Visit is needed, then the following assessments will be performed. Additional assessments can be performed at the Investigator's discretion.

- Concomitant medications including AEDs.
- Vital signs (BP, pulse rate, RR, and temperature).
- AEs.
- Withdrawal criteria
- C-SSRS for subjects ≥ 6 years of age using the version indicated in [Section 10.3.3](#). If an Unscheduled Visit is conducted due to safety reasons, a C-SSRS assessment will be performed with the subject during the visit. If the Unscheduled Visit is conducted for reasons other than safety concerns (eg, replacement of lost medication, repeated collection of a laboratory specimen due to collection or analysis issues), a C-SSRS will not be required at this visit.

9 ASSESSMENT OF PHARMACOKINETIC VARIABLES

The PK sampling will be performed in accordance with the schedule provided in [Table 5-2](#) (15-minute [± 3 minutes] infusion) and [Table 5-3](#) (bolus [up to 2-minute infusion]). Additional PK sampling may be performed at the discretion of the Investigator, especially in the event of a relevant treatment-emergent AE.

Blood samples should be collected after completion of the ECG and the vital sign measurements and from a region of the body not used for the iv BRV administration. The date, start, and stop time of each iv administration and the date and time of each PK sampling must be recorded.

Per subject, the maximum amount of blood collected for PK analyses and clinical laboratory assessments will not exceed a maximum of 3% of the subject's total blood volume within 4 weeks.

Details of plasma sample collection and processing, sample labeling, and shipment will be provided in the laboratory manual.

10 ASSESSMENT OF SAFETY

10.1 Adverse events

10.1.1 Definitions

10.1.1.1 Adverse event

An AE is any untoward medical occurrence in a patient or clinical investigation subject administered a pharmaceutical product that does not necessarily have a causal relationship with this treatment. An AE can therefore be any unfavorable and unintended sign (including an abnormal laboratory finding), symptom, or disease temporally associated with the use of a medicinal (investigational) product, whether or not related to the medicinal (investigational) product.

In order to ensure complete safety data collection, all AEs occurring during the study (ie, after the signing of the ICF/Assent form), including any pretreatment and posttreatment periods required by the protocol, must be reported in the CRF even if no IMP was taken but specific study procedures were conducted. This includes all AEs not present prior to the initial visit and all AEs that recurred or worsened after the initial visit.

Signs or symptoms of the condition/disease for which the IMP is being studied should be recorded as AEs only if their nature changes considerably or their frequency or intensity increases in a clinically significant manner as compared to the clinical profile known to the Investigator from the subject's history or the Baseline Period.

10.1.1.2 Serious adverse event

Once it is determined that a subject experienced an AE, the seriousness of the AE must be determined. A serious adverse event (SAE) must meet 1 or more of the following criteria:

- Death
- Life-threatening
(Life-threatening does not include a reaction that might have caused death had it occurred in a more severe form.)
- Significant or persistent disability/incapacity
- Congenital anomaly/birth defect (including that occurring in a fetus)
- Important medical event that, based upon appropriate medical judgment, may jeopardize the patient or subject and may require medical or surgical intervention to prevent 1 of the other outcomes listed in the definition of serious

(Important medical events may include, but are not limited to, potential Hy's Law [see Section 10.1.1.3], allergic bronchospasm requiring intensive treatment in an emergency room or at home, blood dyscrasias that do not result in inpatient hospitalization, or the development of drug dependency or drug abuse.)

- Initial inpatient hospitalization or prolongation of hospitalization

(A patient admitted to a hospital, even if he/she is released on the same day, meets the criteria for the initial inpatient hospitalization. An emergency room visit that results in

admission to the hospital would also qualify for the initial inpatient hospitalization criteria. However, emergency room visits that do not result in admission to the hospital would not qualify for this criteria and, instead, should be evaluated for 1 of the other criteria in the definition of serious [eg, life-threatening adverse experience, important medical event].

Hospitalizations for reasons not associated with the occurrence of an AE [eg, preplanned surgery or elective surgery for a pre-existing condition that has not worsened or manifested in an unusual or uncharacteristic manner] do not qualify for reporting. For example, if a subject has a condition recorded on his/her medical history and later has a preplanned surgery for this condition, it is not appropriate to record the surgery or hospitalization as an SAE, since there is no AE upon which to assess the serious criteria. Please note that, if the pre-existing condition has worsened or manifested in an unusual or uncharacteristic manner, this would then qualify as an AE and, if necessary, the seriousness of the event would need to be determined.)

10.1.1.2.1 Anticipated serious adverse events

The following Anticipated SAEs are anticipated to occur in the population studied in this protocol at some frequency that is independent of drug exposure.

This list does not change the Investigator’s obligation to report all SAEs (including Anticipated SAEs) as detailed in [Section 10.1.2.3](#).

Table 10–1: Anticipated serious adverse events for the pediatric epilepsy population

MedDRA SOC	MedDRA PT
Congenital, familial and genetic disorders	Teratogenicity
General disorders and administrative site conditions	Sudden unexpected death in epilepsy
Nervous system disorders	Convulsion ^a
	Status epilepticus
Pregnancy, puerperium and perinatal disorders	Abortion spontaneous
Psychiatric disorders	Psychotic behavior
	Abnormal behavior
	Anxiety
	Sleep disorder

MedDRA=Medical Dictionary for Regulatory Activities; PT=preferred term; SOC=system organ class

^a Convulsion if consistent with the seizure type known for the subject.

10.1.1.3 Adverse events of special interest

An AE of special interest is any AE that a regulatory authority has mandated be reported on an expedited basis, regardless of the seriousness, expectedness, or relatedness of the AE to the administration of a UCB product/compound. For this study, the AEs of special interest include:

- Autoimmune nephritis
- Nephritis
- Nephritis allergic
- Tubulointerstitial nephritis
- Tubulointerstitial nephritis and uveitis syndrome
- Potential Hy's Law, defined as $\geq 3 \times \text{ULN}$ ALT or AST with coexisting $\geq 2 \times \text{ULN}$ total bilirubin in the absence of $\geq 2 \times \text{ULN}$ ALP, with no alternative explanation for the biochemical abnormality, must ALWAYS be reported to UCB as an AE of special interest (ie, without waiting for any additional etiologic investigations to have been concluded). Follow-up information should then be reported if an alternative etiology is identified during investigation and monitoring of the subject.

10.1.2 Procedures for reporting and recording adverse events

The subject and/or caregiver (including parent/legal guardian) will be given the opportunity to report AEs spontaneously. A general prompt will also be given at each study visit to detect AEs. For example:

“Did you notice anything unusual about your health (since your last visit)?”

In addition, the Investigator should review any self-assessment procedures (eg, diary cards) employed in the study at each visit.

The AEs should be recorded in the CRF at only the first visit at which they are reported and subsequently only if there is a change.

10.1.2.1 Description of adverse events

When recording an AE, the Investigator should use the overall diagnosis or syndrome using standard medical terminology, rather than recording individual symptoms or signs. The CRF and source documents should be consistent. Any discrepancies between the subject's and/or caregivers own words on his/her own records (eg, diary card) and the corresponding medical terminology should be clarified in the source documentation.

Details for completion of the AE CRF (including judgment of relationship to IMP) are described in the CRF Completion Guidelines.

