7.1.1 Film-coated tablets for oral administration

Tablet strengths: BRV 10mg, 25mg, 50mg, 75mg, and 100mg

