7.1.2 Oral solution

Concentration: BRV 10mg/mL

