7.1.3 Solution for iv injection

Concentration: BRV 10mg/mL

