### 2.3 Study design and conduct

EP0065 is a Phase 2 multicenter, open-label study to evaluate the PK, safety, and tolerability of iv BRV administered as a 15-minute iv infusion and an iv bolus (up to 2-minute infusion) in subjects  $\geq 1$  month to  $< 16$  years of age with epilepsy.

Study medication is defined by iv infusion of BRV administered as a 15-minute iv infusion or an iv bolus (up to 2-minute infusion). Oral BRV can be administered during EP0065 but will not be considered as study medication for EP0065.

Approximately 50 enrolled subjects will receive iv BRV in the following age-based cohorts (approximately 12 subjects/cohort):

- Cohort 1:  $\geq 12$  to  $< 16$  years
- Cohort 2:  $\geq 6$  years to  $< 12$  years
- Cohort 3:  $\geq 2$  to  $< 6$  years
- Cohort 4:  $\geq 1$  month to  $< 2$  years

The age at Screening Visit will be the determining factor for age cohort assignment. Each age cohort will have approximately 50% of subjects with iv BRV infusion and 50% with bolus BRV.

The following subjects will be eligible for enrollment in EP0065:

- Open-label BRV (OLB) subjects: currently receiving oral BRV as participants in a long-term, open-label study
- Prescribed BRV (RxB) subjects: currently receiving prescribed oral BRV from commercial supply
- Initiating Oral BRV (IOB) subjects: not currently receiving BRV; first dose of BRV in EP0065 will be oral tablet or solution
- Initiating iv BRV (IIB) subjects: not currently receiving BRV; first dose of BRV in EP0065 will be by iv Infusion

For OLB and RxB subjects, the maximum BRV dose is 5mg/kg/day (rounded). For IOB and IIB subjects, the maximum BRV dose is 4mg/kg/day. Throughout the study, no subject may receive a dose greater than BRV 200mg/day. Subjects will receive oral BRV (tablets or oral solution) in equally divided doses; BRV oral solution may be given by enteric administration (eg, by feeding tube) based on subject need.

The EP0065 study periods and visits are described below. The PK assessments will be made during the iv PK Period only and safety data will be collected throughout the study, with intensive collection of safety data with each iv BRV dose administered. A Schedule of Study Assessments is provided in the protocol for the Screening through iv PK Periods and for the Down-Titration Period and Safety (BRV-free) Periods (for subjects not continuing BRV).

- Screening Period (1 to 10 days)

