### Imputation of Partial AE End Dates

- If only the month and year are specified, then use the last day of the month.
- If only the year is specified, then use 31 Dec of that year.
- If the AE resolved and the resolution date is completely unknown, then do not impute the resolution date.

In the event of ambiguity or incomplete data which makes it impossible to determine whether an AE was treatment emergent or not, the AE will be considered as treatment emergent.

With respect to AEs, events with missing intensity will be assumed to be severe. Events with missing relationship to iv BRV per the investigator will be assumed to be related.

Data handling for worsened AEs is provided below. The standard AE eCRF has the outcome of “worsened” to be used when there is an increase in the intensity of an AE. The definition of “worsened” is when the AE is still present but at a heightened intensity. The eCRF instructions dictate to complete a new AE screen with the event term of the worsened event.

Note that the outcome of “worsened” is not allowed terminology within the CDISC standards. In the SDTM.AE, the data is mapped to the outcome “Not Recovered/Not Resolved”. The outcome of “Worsened” will be kept in SDTM.SUPPAE. For subject data listings, the convention will be used to map SDTM terminology of “Not Recovered/Not Resolved”.

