## 10.2 Adverse Events

All adverse events (AEs) occurring during EP0065 (ie, after signing of the ICF) must be reported. For subjects who transition to study N01266, any AEs which began after the first dose of BRV in N01266 but prior to TC-1 of EP0065 will be considered as during EP0065 and N01266. Pre-treatment adverse events (PTAEs) are defined as AEs that had onset strictly prior to the date/time of the first BRV medication taken during EP0065. For OLB subjects, where the AE started prior to EP0065 enrollment, information will come from the respective OLB study.

Treatment-emergent adverse events (TEAEs) are defined as those events which started on or after the first BRV medication taken during the EP0065 study. Subjects who began the study on BRV treatment (OLB and RxB subjects) will be assumed to have taken BRV treatment on the first day of screening. Timing of an AE being treatment emergent varies by subject group: all AEs are treatment emergent for RxB and OLB subjects; all AEs on or after the IOB Treatment Period are treatment emergent for IOB subjects; all AEs on or after the iv PK Period are treatment emergent for IIB subjects.

Data handling rules for management of missing or partial start or stop dates for adverse events should follow those defined in the [Section 4.2.4](#). The classification of TEAE will be done after imputation of any partial start dates.

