### 10.2.1 AE summaries

All AE tables will be summarized separately over all AEs and by MedDRA SOC and MedDRA PT. The number and percentage of subjects experiencing each event at least once will be summarized. All summaries will be sorted alphabetically by SOC and by frequency of events within PTs, starting with the most frequent event overall. All summaries are for all study periods combined (Screening, IOB treatment, iv-PK, Follow-up, and Safety (BRV free) Period) unless otherwise indicated. Only the first occurrence of a TEAE of a particular PT will be included in incidence calculations, but all occurrences of TEAEs of the same PT will be included in counts of TEAEs. For summaries by study period, AEs are assigned only to the period on which they began. TEAEs of interest is a selection of TEAEs identified by UCB to be of interest to BRV.

The following summaries will be produced overall and by age cohort, for all subjects and separately by infusion duration, and subject group for the SS-iv:

- Incidence of AEs – Overview (number and percentage of subjects with at least one: AE, TEAE, serious TEAE, non-serious TEAE, TEAE of interest, TEAE requiring dose change,

drug-related TEAE, drug-related serious TEAE, and severe TEAE, as well as the number and percentage of subjects who discontinued due to a TEAE, had permanent withdrawal of BRV due to a TEAE, had an AE leading to death, and had a TEAE leading to death)

- Incidence of TEAEs
- Incidence of TEAEs Leading to Study Discontinuation
- Incidence of Serious TEAEs

The following AE summaries will be produced overall and by age cohort, for all subjects and separately by infusion duration for the SS-iv:

- Incidence of PTAEs
- Incidence of TEAEs by Maximum Intensity  
Each subject will be counted at most once per primary SOC or PT according to the maximum intensity of all AEs within that SOC or PT. Severe intensity will be assumed for AEs for which intensity is not specified.
- Incidence of TEAEs by Maximum Relationship  
Drug-related AEs are AEs for which the relationship to trial medication is specified as related or AEs for which relationship is not specified.
- Incidence of TEAEs of Interest
- Incidence of Non-serious TEAEs Occurring in at least 5% of Subjects
- Incidence of Serious TEAEs by Relationship to BRV
- Incidence of Fatal TEAEs by Relationship to BRV

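### The SS-iv drug-related AE tables count events that began before any infusion; Protocol 12.4.1.1 planned that summary for the iv PK Period, and SAP 3.10 does not list the change

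*Protocol*

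**What the plan says.** **Scope in the Protocol.** Section 12.4.1.1 plans the primary safety variables (AEs and withdrawals due to AEs) on the SS-iv for the iv PK Period. It adds AE summaries by study period on the SS and by epoch around the infusion on the SS-iv.

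**Causality in the Protocol.** Section 10.1.2.1: "Details for completion of the AE CRF (including judgment of relationship to IMP) are described in the CRF Completion Guidelines". Section 7.1 describes three IMPs, under the headings "7.1.1 Film-coated tablets for oral administration", "7.1.2 Oral solution" and "7.1.3 Solution for iv injection".

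**Treatment in the SAP.** Section 2.3: "Oral BRV can be administered during EP0065 but will not be considered as study medication for EP0065".

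**TEAE start in the SAP.** Under section 10.2 the treatment-emergent clock starts at the first BRV taken in EP0065, whatever the route. OLB and RxB children are assumed to have taken BRV on the first day of screening, so "all AEs are treatment emergent for RxB and OLB subjects". For IOB children the clock starts with the IOB Treatment Period, and for IIB children with the iv PK Period.

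**Tables in the SAP.** Section 10.2.1 pools Screening, IOB treatment, iv PK, Follow-up and Safety Periods unless a table says otherwise. On the SS-iv, by infusion duration, it plans an Overview (with drug-related and drug-related serious rows), TEAEs by Maximum Relationship, and Serious and Fatal TEAEs by Relationship to BRV. Its definition is: "Drug-related AEs are AEs for which the relationship to trial medication is specified as related or AEs for which relationship is not specified". Section 4.2.4 adds: "Events with missing relationship to iv BRV per the investigator will be assumed to be related".

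**Declared changes.** SAP 3.10 covers the PK-PPS definition, vital sign and ECG time points, and the replacement of AE epochs by time since the most recent infusion start. It does not mention extending the SS-iv AE tables beyond the iv PK Period.

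**The concern.** The primary objective concerns BRV given as a 15-minute infusion and as a bolus, and the SS-iv is the primary safety set. A drug-related count in the bolus column will be read as a reaction to the bolus. If the event began on oral BRV, before any infusion, it sits in that column only because of an infusion given later.

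The rows also cover different spans by subject group. OLB and RxB children contribute Screening and IOB children contribute oral treatment, while IIB children contribute nothing before the infusion. Two infusion-duration columns with different mixes of subject groups could differ for that reason alone. All summaries are descriptive, so these counts are themselves the reported safety result.

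**Working it through.** No figure in the plan needs to be reproduced. The check follows the rules for an event that began before the first infusion in a child who later received iv BRV.

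| Group | Onset | Status (SAP 10.2) | Judged related | Causality blank | Judged not related |
|---|---|---|---|---|---|
| OLB, RxB | Screening | TEAE | counted | counted | not counted |
| IOB | IOB Treatment Period | TEAE | counted | counted | not counted |
| IIB | Screening | PTAE | not counted | not counted | not counted |

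Here, counted means included as drug-related in the SS-iv tables. No rule in SAP 4.2.4, 10.2 or 10.2.1 removes an onset before the first infusion.

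**What other planned outputs recover**

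- *Maximum Relationship.* SAP 10.2.1 also plans this table by study period and infusion duration, on the SS. SAP 3.2.5 starts the iv PK Period at the first iv dose, so only SS-iv children can have events in it. The iv PK Period numerators are therefore those of the SS-iv.
- *Overview, and Serious and Fatal by Relationship.* None is planned by period. Serious TEAEs are tabulated by period, but not by relationship.
- *Time since previous infusion.* The categories start at 0 minutes, there is none for events before the first infusion, and the table is not split by relationship.

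**Time window.** The inputs are Screening of 1 to 10 days for OLB and RxB, IOB treatment of 2 to 10 days, 1 to 10 iv doses, and an iv PK Period ending 12 hours after the start of the last dose. At a nominal 12-hour interval the iv PK Period lasts 0.5 × doses, that is 0.5 to 5 days. The pre-infusion share of treatment-emergent time is pre / (pre + post).

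Up to the end of the iv PK Period:
- OLB and RxB: 1/(1 + 5) = 17% to 10/(10 + 0.5) = 95%.
- IOB: 2/(2 + 5) = 29% to 10/(10 + 0.5) = 95%.

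Over the whole pooled span for OLB and RxB:
- Low end, with 10 doses, 28 days of down-titration and 14 BRV-free days: 1/(1 + 5 + 42) = 2%.
- High end, with one dose and TC-1 one day later: 10/(10 + 1) = 91%.

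These are shares of time, not of drug-related events. The documents give neither AE counts nor a rate of missing causality.

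**Weight of one child.** With about 12 per cohort and half on each infusion duration, a cell holds about 12/2 = 6, so one child is 1/6 = 17 percentage points. With about 50 in all, an infusion-duration column holds about 50/2 = 25, so one child is 1/25 = 4 points. This applies only if the child has no drug-related TEAE after the infusion started; otherwise the child is already in that row.

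**The case against.** The strongest reply is that the plan is conservative and the information is available elsewhere. Counting blank causality as related can only raise the drug-related count. OLB and RxB children are taking BRV during Screening, so relating a Screening event to BRV is not absurd. The Overview is also shown by subject group, and its IIB part contains no pre-infusion TEAEs. The by-period table settles Maximum Relationship, and the listings give onset time, relationship and time since the previous infusion.

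Much of this stands, and it limits the point. It does not repair the Overview or the serious and fatal relationship tables, where pre- and post-infusion events stay merged under an infusion-duration heading.

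A reader might go further and infer that the mismatch between IMP in the Protocol and iv BRV in the SAP produces the miscount. The documents do not support that:

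- The AE form is not among them, so the wording of its causality field cannot be confirmed.
- The SAP's own wording varies between iv BRV, trial medication, study medication and BRV.
- Renaming the field changes no count. Events enter through the any-route TEAE start and the pooled periods.
- It is unclear whether the oral BRV that OLB and RxB children take during Screening, from open-label or commercial supply, is IMP of this study.

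**Conclusion.** The SS-iv drug-related tables extend to time before the first infusion, against the scope in Protocol 12.4.1.1 and without an entry in SAP 3.10. The affected events are those in OLB, RxB and IOB children that began before any infusion and were judged related or have blank causality. It would be wrong to infer that every pre-infusion event counts as drug-related: IIB events and events judged not related do not.

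The defect remains in the Overview and in the Serious and Fatal by Relationship tables. For Maximum Relationship it is mitigated by the by-period version. The number of affected events is unknown. The time shares of 2% to 91% over the pooled span, or 17% to 95% up to the end of the iv PK Period, are too wide to serve as an estimate. What can be said is that cells are small, so a single event can matter.

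The varying causality term is a lesser fault of clarity. Its one substantive consequence is that SAP 4.2.4, read literally, relates a blank-causality event to iv BRV before any was given.

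**What to change.** 1. In the SS-iv Overview and in the Maximum Relationship, Serious by Relationship and Fatal by Relationship tables, count drug-related TEAEs with onset at or after the first infusion. Show earlier ones in a separate row labelled *before first infusion*, so that no event is lost.
2. In SAP 3.10, record any scope that still differs from Protocol 12.4.1.1. After step 1 the rows would still include Follow-up and the Safety Period.
3. Use one causality reference term in SAP 4.2.4, 10.2.1 and 10.2.2, matched to the field actually collected.
4. In SAP 4.2.4, do not label blank causality as related to iv BRV when onset precedes the first infusion. It may remain related to BRV.

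The cost is SAP wording and one extra row per table. No new data are needed, since onset and infusion times are already recorded. Steps 3 and 4 alone would leave the drug-related counts unchanged; step 1 is the one that matters.
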